6.c. Risk:Benefit Analysis of study interventions being tested or evaluated under this protocol

For each study intervention identified in section 6b above, complete a risk:benefit analysis table.

(Two tables are provided, copy & paste additional tables as needed or delete both tables if this study does not test an intervention)

6.c.		
Study Intervention #1 Sevelamer carbonate		
List each group exposed to this		
intervention on a separate line. (e.g., experimental, control, Arm A, Arm etc Or state All Groups/Subjects	B, the interventi	up, list the benefits of this intervention. (Benefits can be directly from on or from a monitoring procedure likely to contribute to the subject's If there are no benefits, state "none".
Experimental Sevelamer	decrease pla	diabetic and obese type 2 diabetic subjects, sevelamer could sma cholesterol level and improve insulin sensitivity. In obese type 2 ects, sevelamer also could improve plasma glucose level.
(include: 1) expected adverse events; 2)	(likely, less likely or r rare and serious adv	are) and magnitude (serious or not serious). erse events; 3) all other psychological, social, legal harms) omptly later = a requirement to estimate frequency (Instructions).
Likely	Nausea	•
These risks are expected to occur in more than 20 out of 100 subjects.	Vomiting	
	Not serious	Serious
Less likely These risks are expected to occur in 5- 20 subjects or less out of 100 subjects.	 Diarrhea Dyspepsia Abdominal Pain Flatulence Constipation 	
		Serious
Rare These risks are expected to occur in less than 5 subjects out of 100		 -Fecal impaction, bowel obstruction or bowel perforation: Sevelamer is a very safe drug; its main side effects are gastrointestinal. In a large trial, 1053 subjects with chronic kidney disease received sevelamer (Suki et al Kidney Int. 2007 Nov;72(9):1130-7). Three related serious adverse events occurred in three subjects: constipation, vomiting, and osteoporosis. The subject diagnosed with osteoporosis was a 72-year-old woman who had been treated intermittently for asthma with both oral and inhaled steroids. Subjects with active gastrointestinal disease, or history of gastrointestinal obstruction and/or surgery within the last 2 years, will be excluded. -Hypophosphatemia. Sevelamer does not cause hypophosphatemia in subjects with normal kidney function. As an extra precaution, we will only enroll subjects with normal phosphorus plasma concentration, which will be monitored during treatment.

6.c.				
Study Intervention #2				
Synbiotic (Bifidobacterium longum and ol	igofructose)			
List each group exposed to this				
intervention on a separate line.	For each gro	For each group, list the benefits of this intervention. (Benefits can be directly from		
(e.g., experimental, control, Arm A, Arm E		the intervention or from a monitoring procedure likely to contribute to the subject's		
etc	well being).	well being). If there are no benefits, state "none".		
Or state All Groups/Subjects				
Experimental/ Synbiotic	decrease pla	In obese nondiabetic and obese type 2 diabetic subjects, the synbiotic could decrease plasma cholesterol level and improve insulin sensitivity. In obese type 2 diabetic subjects, the synbiotic also could improve plasma glucose level.		
For this intervention, list the reasonably foreseeable risks List the risks according to the probability (likely, less likely or rare) and magnitude (serious or not serious). (include: 1) expected adverse events; 2) rare and serious adverse events; 3) all other psychological, social, legal harms) Do not delete frequency. The need to know what to report promptly later = a requirement to estimate frequency (Instructions).				
	Not serious	Serious		
Likely	•	•		
These risks are expected to occur in				
more than 20 out of 100 subjects.	Not serious	Serious		
1	Bloating			
These risks are expected to occur in 5-	Diodiling			
20 subjects or less out of 100 subjects.				
		Serious		
Rare		•		
These risks are expected to occur in				
less than 5 subjects out of 100				

		6.d . List of ALL other All of the rese			not listed in table 6.b. I be listed in either table 6.b. or 6.d.
		Consider grouping sin assessments)	nilar procedures unde	r a single compo	onent. E.g., blood work, CT = safety
		(Click here for exam	ple)		
#	Research component • individual	Column A Local Standard	Column B Research Only	Column C	Column D Risks
	example: Eligibility Assessments • History and physical • Questionnaire • Laboratory tests Add or delete rows as needed	Practice Indicate the number of times each procedure will be performed as stipulated in the research plan that would be done as part of standard practice.	Indicate the number of times each procedure will be performed solely for research purposes (any performed outside frequency or timing for acceptable local practice)	performed at the VA	List the reasonably expected risks under the following categories as appropriate: Serious and likely; Serious and less likely; Serious and rare; Not serious and likely; Not serious and less likely
1	Eligibility				
	Consent	0	1		None
	Medical History, Inclusion/Exclusion Review	0	1	\checkmark	None
	Physical Exam/assessment	1	0	V	None
	Screening blood tests (chemistry, CBC, lipid profile, A1c, PT,PTT)	0	1	\checkmark	Not serious and likely: momentary pain and discomfort during venipuncture bleeding, bruising and infection
	Screening urine analysis	0	1	√	None
	75 gm oral glucose tolerance test including venipuncture	0	1	\checkmark	Not serious and likely: Pain: momentary pain and discomfort during venipuncture. bleeding, bruising and infection Blood loss: 50 ml
2	Safety Assessment				
	ECG	0	1	\checkmark	None
3	Research Assessment				
 	Pharmacological intervention (placebo, symbiotic, or Sevelamer)	0	2	\checkmark	See section 6c
	Blood LPS	0	4	\checkmark	Not serious and likely: momentary pain and discomfort during venipuncture bleeding, bruising and infection
	Stool sample	0	4	V	None
	Intestinal permeability test	0	2	V	None
	DEXA	0	2	\checkmark	Not serious and likely: Subjects will be exposed t a very small amount of radiation during the DEXA exam (0.1 mrem/DEXA). Rare and serious: cancer
	Euglycemic insulin clamp	0	2	V	Not serious and likely: Pain: momentary pain and discomfort during venipuncture. bleeding, bruising and infection Rare and serious: cancer Radiation.2 Clamps: Tritiated glucose is given during the clamp. The radiation exposure is minimal (19.7 mRem/clamp) which is well within guidelines. Blood loss: 100 ml

				Not serious and less likely: Hypoglycemia is possible; however, since the glucose infusion is designed to counterbalance the metabolic effects of insulin, hypoglycemia will not occur. No other side effects of insulin and glucose are known. Plasma glucose concentration will be determined at 5 minute intervals throughout the period of insulin/glucose administration. The 20% dextrose infusion will be adjusted in order to maintain euglycemia (100 mg/dl) and to avoid hypoglycemia.
Direct calorimetry (ventilated hood) during insulin clamp	0	4	\checkmark	Not serious and less likely: Claustrophobia
Hot box during insulin clamp		2		Serious and rare: burns and blisters
Muscle biopsy (thigh)	0	4		Not serious and likely: Pain: At the time of biopsy, subjects may feel mild pain, discomfort, or pressure (variably described by different subjects) for about 5-10 seconds. Pain or discomfort ceases as soon as the biopsy needle is withdrawn. Local hematomas: Local hematomas occur rarely and they resolve spontaneously within 2 weeks. Less Likely and Serious: Allergy: Allergic reactions to the local anesthetic (lidocaine) are extremely rare, but could include dermatitis, swelling, or hives. None of our patients have experienced any serious allergic reaction to the local anesthetic. Serious and rare: Bleeding from a muscle biopsy may be severe enough to require hospitalization. This has occurred in less than 1 in 500 of these pro Numbness Very rarely some subjects may experience numbness or tingling at the biopsy site. This usually is temporary and goes away in a few days. There is the possibility, less than 1 in 1000, that nerve damage could be permanent. cedures. Infection: There is a small risk, less than 1 in 100, of infection at the site of the muscle biopsy. Symptoms of an infection would include pain, redness, swelling, and yellow-greenish (pus- looking) discharge in the biopsy site, and is usually accompanied by fever. Because 4 biopsies of the muscle will be performed, the risk of infection and pain in the leg may increase. Infections can be usually treated effectively with antibiotics taken by mouth. In very rare occasions, hospitalization is required to give antibiotics through the vein, and an operation could be needed to clean the infected area. Permanent nerve damage: Permanent nerve damage manifested as localized numbness or decreased sensation is possible, but very rare.

7. Safety Precautions. (Describe safeguards to address the serious risks listed above.)

a. Describe the procedures for protecting against or minimizing any potential risks for each of the more than minimal risk research procedures listed above.

Risks will be minimized by a careful screening process including medical history, physical exam, and review of complete blood count, coagulation tests, chemistry and electrocardiogram. The presence of experienced personnel, and of at least one physician, at all times is also critical to reducing risks.

Insulin Clamp: Plasma glucose concentration will be determined at 5 minute intervals throughout the period of insulin/glucose administration. The 20% dextrose infusion will be adjusted in order to maintain euglycemia (100 mg/dl) and to avoid hypoglycemia.

Muscle biopsies: To avoid local hematoma formation, pressure is applied for 30 min after the biopsy. To avoid infection, the procedure is performed under sterile conditions. Our group has experience with over 1000 biopsies.

Blood loss: The total amount of blood drawn will be less than 500 ml. The subjects will be told that they should not donate blood for two months after the study. Any subject with a hematocrit of less than 34% will not be studied.

b. Where appropriate, discuss provisions for ensuring necessary medical or professional intervention in the event of adverse events, or unanticipated problems involving subjects.

Any expected or unexpected adverse events will be assessed by [name] or a co-investigator. Any necessary immediate medical care will be arranged in conjunction with the subject's wishes.

c. Will the safeguards be different between/among groups?

Х

If yes, describe here

8. Confidentiality of the Research Information

Yes

a. Specify where the data and/or specimens will be stored and how the researcher will **protect the confidentiality** of subject information. *If you will be collecting Social Security Numbers* (SSNs), Scrambled Social Security Numbers, or the last four digits of a Social Security Number, provide details regarding the **security measures** to protect the SSNs.

Data will be coded with a series of numbers unrelated to the SSN. The key to the link will be stored in a separate location. All data will stored in password-protected VA computer at the Bartter Research Unit under the VA server. Electronic files will be stored on STX_Research\PI_MusiN study folders. Paper research records will be stored in locked cabinet in a locked office on BRU until completion then moved to GRECC A300 for data analysis and permanent storage.

The Specimens will be stored in a restricted access area at the Bartter Research Unit laboratory

No

b.	. Will all electronic data be stored in accordance with the institution's information security policy and encryption standards?				
	X Yes		No, if no explain below		

9. Payment.

(payment of subjects should be included in the consent form)

a. Describe the incentives (e.g., inducements) being offered to subjects for their time during participation in the research study.

The subjects will receive monetary compensation to cover their time and transportation costs

b. If monetary compensation is offered, indicate how much the subjects will be paid and describe the terms and schedule of payment.

IRB policy requires a provision for providing partial payment to subjects who withdraw before the completion of the research. For VA research, payment to human subjects participating in research is prohibited when the research is integrated with the patient's medical care and when the research makes no special demands on the patient beyond those of standard medical care. Payment may be permitted, with IRB approval, under certain circumstances. Consult with the VA R&D Office to discuss payment of subjects.

Subjects will receive :

- \$50 after Visit 2 (glucose tolerance test).
- \$50 after Visit 3 (intestinal permeability test).
- \$300 after Visit 4 (insulin clamp and muscle biopsy).
- \$50 after Visit 5 (intestinal permeability test).
- \$300 after Visit 6 (insulin clamp and muscle biopsy).

On rare occasions we may agree to reimburse you for unexpected or unusual expenses related to travel or other circumstances related to study participation, but this may not exceed \$100. This will be done on an individual basis only and will be subject to approval by the Principal Investigator [name].

10. Costs to Subjects.

(costs to the subject should be included in the consent form)

a. Describe any costs for care associated with research (including a breakdown of standard of care procedures versus research procedures), costs of test drugs or devices, and research procedure costs that are the subject's responsibility as a consequence of participating in the research.

There will be no cost to study volunteers. Some veterans are required to pay co-payments for medical care and services provided by the VA. These co-payment requirements will continue to apply to medical care and services provided by the VA that are not part of this study. There will be no cost to veterans or non-veterans for procedures and drugs that are part of this research study.

b. Describe any offer for reimbursement of costs by the sponsor for research related injury care. (Attach a copy of the section of the clinical trial agreement or contract describing research related injury care – the information in this section must match the injury section of the consent form).

In the event that you sustain an injury or illness as a result of your participation in this VA approved research, all medical treatment (emergency as well as medical treatment beyond emergency care) will be provided by the VA. You will be treated for the injury at no cost to you. However, no additional compensation has been set aside. You have not waived any legal rights or released the hospital or its agents from liability for negligence by signing this form.

11. PI-Sponsored FDA-Regulated Research If the PI is the IND/IDE holder, or has agreed to perform any of the IND/IDE holder's sponsor obligations, the PI is considered a sponsor (sponsor investigator) and must meet additional requirements. (Form O, O-1 and P provide details) [see Office of Clinical Research policies]				
X N/A. The PI is not the IND or IDE holder, or has not agreed to perform sponsor obligations				
a. Has the PI completed the CITI module: Conducting Investigator-Initiated Studies According to FDA Regulations and	d Good			
Clinical Practices?				
X Yes No. If no, complete the training prior to submitting this protocol				
b. Describe the PI's experience/knowledge/training related to serving as a sponsor-investigator.				
Describe here				

Abstract / Project Summary

Provide a succinct and accurate description of the proposed research. State the purpose/aims. Describe concisely the research design and methods for achieving the stated goals. This section should be understandable to all members of the IRB, scientific and non-scientific. This summary will also be needed in future IRB Progress Reports.

DO NOT EXCEED THE SPACE PROVIDED.

Purpose/Objectives: Insulin resistance in peripheral tissues (i.e. skeletal muscle) is one of the earliest and most significant abnormalities in the pathogenesis of type 2 diabetes (T2DM). However, the molecular basis for the insulin resistance of T2DM is not fully understood. The human gut hosts an enormous number and variety of microorganisms, including at least 1014 bacteria. An increasing number of animal studies suggest that this microbial "organ", also known as the microbiome, is a causative factor in the insulin resistance of obesity and T2DM, and may represent an entirely new therapeutic target against these conditions. These studies suggest that high fat ingestion, obesity, and T2DM, favor a microbiome profile which enhances production and gastrointestinal permeability of lipopolysaccharide (i.e. metabolic endotoxemia). Lipopolysaccharide (LPS or endotoxin) is a component of the outer membrane of gram negative bacteria cell walls which induces an inflammatory response by activating the cell surface receptor toll-like receptor-4 (TLR4). Despite accumulating evidence from animal studies suggesting that intestinal microbiome and metabolic endotoxemia on human metabolic disease remains unknown. Thus, the goal of this study is to determine the role that intestinal microbiota and metabolic endotoxemia play in the pathogenesis of insulin resistance and T2DM in humans.

Research Design/Plan: We will study three groups of subjects: 1) 36 healthy, 18-65 yrs old, normal-glucose tolerant subjects, without a family history of T2DM, and body mass index (BMI) of \leq 26 kg/m²; 2) 36 obese, 18-65 yrs old, normal-glucose tolerant subjects, with or without a family history of T2DM, and body mass index (BMI) of 30-37 kg/m²; 3) 36 obese, 18-65 yrs old, T2DM with or without a family history of T2DM, HbA1C \leq 8.5%, and body mass index (BMI) of 30-37 kg/m². All subjects will undergo pharmacological intervention. All subjects will be studied at the Bartter Research Unit (BRU) at the Audie L. Murphy VA Medical Center, as follows;

Visit 1: Screening tests including a complete history and physical examination/assessment, ECG, blood chemistry, blood cell count, HbA1c, PT, PTT, lipid profile, and UA.

Visit 2: OGTT.

Visit 3: Stool sample collection, plasma LPS measurement, and an 8 h intestinal permeability (lactulose/mannitol) testing.

Visit 4: DEXA, euglycemic hyperinsulinemic clamp, and indirect calorimetry. At time -30 min a biopsy of the vastus lateralis muscle will be performed. At time 0 min, insulin will be infused at 60 mU/m2.min for 180 min. A 2nd biopsy is performed on the contralateral leg at 180 min.

Pharmacological/nutraceutical intervention: Subjects will be randomized to receive, in a double-blind fashion, placebo (maltodextrin, 6 g three times a day), the synbiotic [5 g of oligofrucose + 1 g Bifidobacterium longum (4x10^10 CFU/g) three times a day], or sevelamer (1.6 g sevelamer + 4.4 g maltodextrin three times a day), for 4 weeks. For each dose the powder will be included in identical packets. The subjects from the 3 groups (placebo, synbiotic, sevelamer) will ingest the powder contained in one packet with water 3 times /day for 28 days.

Visit 5: Stool collection, plasma LPS measurement, and intestinal permeability testing as described above for visit 3.

Visit 6: DEXA, insulin clamp, indirect calorimetry, and biopsies of the muscle (2) as described above for Visit 4.

Clinical Relevance: Our findings will improve our understanding of the key role that the microbiome and endotoxemia play in the pathogenesis of insulin resistance. This new knowledge could lead to the development of novel therapies for T2DM.

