Analyses. Plasma LPS, LBP, soluble CD14, IL-6, TNF α and phosphate will be measured before, during, and after treatment (Visits 3, 4, 5 and 6). Assays of TLR4 and insulin signaling in muscle are performed as described for Aim 1. Stool samples will be collected before and during treatments. This will allow us to evaluate differences in microbiome composition between lean, obese, and T2DM subjects at baseline, and establish the relationship between treatment-induced changes in specific bacteria composition/distribution with changes in inflammation and insulin action.

4. Study Population(s).

You will be drawing subjects from one or more populations. In medical research, for example, a population can be individuals with type 2 diabetes controlled with diet, or a population of healthy individuals. In social behavioral research, a population can be individuals attending an education program, etc.

4.a. How many different populations are you enrolling in this study?	3
4.b. For each different population, provide a short descriptive label : (e.g., normal-healthy, diabetics, parents, children, etc.) Copy and paste additional labels as needed →	 Lean nondiabetic Obese nondiabetic Obese type 2 diabetic

4.c.	4.c. For each specific population identified in 4b, provide the following information in the table provided below.				
	(For studies with more than one population, copy all of table 4.c. and paste to insert additional tables.)				
Population # 1 Population Descriptive Label: Lean nondiabetic		Population Descriptive Label: Lean nondiabetic			
(1) Identify the criteria for inclusion:		e criteria for inclusion :			

#	HSC20130458H		
1) Bo 2) All 3) Pro 4) Po 5) HC 6) Sta 7) Tw 8) BM	th genders between ages 18-65 years, without family history of diabetes. races and ethnic groups. emenopausal women in the follicular phase, non-lactating, and with a negative pregnancy test. stmenopausal women on stable dose of or not exposed to hormone replacement for \geq 6 months. CT \geq 34%, serum creatinine \leq 1.4 mg/dl, electrolytes, urinalysis, and coagulation tests. LFTs up to 2X. able body weight (±2%) for \geq 3 months. γ or less sessions of strenuous exercise/wk for last 6 months η <26 kg/m2 rmal glucose tolerance based on ADA criteria		
(2)	Identify the criteria for exclusion :		

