2) Fa 3) Cu past 3 recep 4) His 5) No 6) Cu held 1 7) Us 8) His on th 9) Po 10) A	 Presence of impaired glucose tolerance or type 2 diabetes based on ADA criteria Family history of diabetes (parents, siblings, children) Current treatment with drugs known to affect glucose and lipid homeostasis. If the subject has been on a stable dose for the past 3 months, the following agents will be permitted: calcium channel blockers, beta-blockers, ACE inhibitors, angiotensin receptor blockers, and statins. History of allergy to sevelamer. Non-steroidal anti-inflammatory drugs or systemic steroid use for more than a week within 3 months. Current treatment with anticoagulants (warfarin). Aspirin (up to 325 mg) and clopidogrel will be permitted if these can be held for seven days prior to the biopsy in accordance with the primary physician. Use of agents that affect gut flora (e.g. antibiotics, colestyramine, lactulose, PEG) within 3 months. History of heart disease (New York Heart Classification greater than grade II; more than non-specific ST-T wave changes on the ECG), peripheral vascular disease, pulmonary disease, smokers. Poorly controlled blood pressure (systolic BP>170, diastolic BP>95 mmHg). Active inflammatory, autoimmune, hepatic, gastrointestinal, malignant, and psychiatric disease. 		
,	istory of gastrointestinal surgery or gastrointestinal obstruction within two years. Recruitment Process – identifying potential subjects		
(3)	Describe plans about how the population will be identified for the purpose of recruiting. (e.g., database search, personal contacts, referrals, patients under the care of the research team, etc.) (Consider Form J, HIPAA Waiver to access PHI for identification of potential subjects)		
All su	bjects will be recruited through advertisement in local newspapers, radio and the web.		

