	 Current treatment with drugs known to affect glucose and lipid homeostasis (sulfonylureas only are permitted). If the subject has been on a stable dose for the past 3 months, the following agents will be permitted: calcium channel blockers, betablockers, ACE inhibitors, angiotensin receptor blockers, and statins. History of allergy to sevelamer. BMI <30 or >37 kg/m2 Non-steroidal anti-inflammatory drugs or systemic steroid use for more than a week within 3 months. Current treatment with anticoagulants (warfarin). Aspirin (up to 325 mg) and clopidogrel will be permitted if these can be held for seven days prior to the biopsy in accordance with the primary physician. Use of agents that affect gut flora (e.g. antibiotics, colestyramine, lactulose, PEG) within 3 months. History of heart disease (New York Heart Classification greater than grade II; more than non-specific ST-T wave changes on the ECG), peripheral vascular disease, pulmonary disease, smokers. Poorly controlled blood pressure (systolic BP>170, diastolic BP>95 mmHg). 					
	9) Act	tive inflamn	natory, autoimmune, hepatic, gastrointestinal, malignant, and psychiatric disease.			
	10) H		strointestinal surgery or gastrointestinal obstruction within two years.			
	(3)	Describe	ent Process – identifying potential subjects plans about how the population will be identified for the purpose of recruiting. (e.g., database search, contacts, referrals, patients under the care of the research team, etc.)			
		-	Form J. HIPAA Waiver to access PHI for identification of potential subjects)			

FO	RM	С

Subjects	will	be	re
	Subjects	Subjects will	Subjects will be

HSC20130458H

IRB #

Г

Clinic or the	ects will be recruited through advertisement in local in local newspapers and the web, and through the General Medicine is of the University Center for Community Health and the Audie L. Murphy VA Hospital. Patients who present to the clinic e VA will have their chart reviewed to determine if the hey meet inclusion criteria. A HIPAA Waiver and a Waiver of ent will be requested for this activity.					
	If recruiting from more than one institution and the identification process differ - clearly describe differences here.					
	New participants will first contact the researchers. The research team will then make an appointment to explain the study to the participant					

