Choose one of the choices below:					
		There is no expected direct benefit for those participating. (go to $c(1)$ and $c(2)$ below)			
There is an expected direct benefit for those participating. Provide justification why the delay is acceptable below , then (go to c(1) and c(2)below)					
Insert the reason a delay is acceptable here					
		e recruiting non-English speaking subjects, Describe the process for obtaining informed consent from bjects in their respective language (or the legally authorized representative's respective language).			
Describe here					
		to ensure that individuals are appropriately informed about the study when English is their second-language n for evaluating the level of English comprehension, and the threshold for providing a translation, or explain			

6. Research Plan / Description of the Research Methods:

6.a. Provide a **comprehensive narrative** describing the **research methods**.

Provide the order in which tests/procedures will be performed,

the setting for these events and a description of the methods used to protect privacy during the study.

Provide the **plan for data analysis** (include as applicable the **sample size calculation**)

Visit 1: Subjects will come to the BRU at 7 AM for a medical history, physical examination (including anthropometric measurements), screening tests (CBC, chemistry, lipid profile, HbA1c, PT, PTT, UA, pregnancy test if applicable), and ECG.

Visit 2: Within 3-14 days from Visit 1, eligible subjects will return at 7 AM after an overnight fast for an oral glucose tolerance test (OGTT).

Visit 3: Within 3-21 days from Visit 2, subjects will come to the BRU at 7 AM in the fasting state to undergo stool sample collection, plasma LPS, LBP measurement, inflammatory markers and phosphate (see Analyses page 11), and an 5h intestinal permeability (lactulose/mannitol) test. Serum phosphorus also will be measured.

Visit 4: Within 7-21 days from Visit 3, subjects will undergo whole body DEXA, a euglycemic hyperinsulinemic clamp and indirect calorimetry as described (44, 45). A pregnancy test is performed if applicable. DEXA is performed to examine the effect of the interventions on body composition. At time -30 min a biopsy of the vastus lateralis muscle will be performed. At time 0 min, insulin will be infused at 60 mU/m2.min for 180 min. A 2nd biopsy is performed on the contralateral leg at 180 min. Labs for analyses as in Visit 3 are repeated.

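### Is the normal-phosphorus enrolment condition in Section 6.c lost because the eligibility lists in Section 4.c do not repeat it?

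*Combined protocol and SAP*

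**What the plan says.** Section 6.c (Study Intervention #1, sevelamer, rare serious risks) lists hypophosphatemia. It says that sevelamer does not produce it when kidney function is normal, and then adds: "As an extra precaution, we will only enroll subjects with normal phosphorus plasma concentration, which will be monitored during treatment". The same cell carries a second precaution, that subjects with active gastrointestinal disease or a "history of gastrointestinal obstruction and/or surgery within the last 2 years, will be excluded".

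The inclusion lists in Section 4.c cap serum creatinine at 1.4 mg/dl for all three populations and include a laboratory item that reads "electrolytes, urinalysis, and coagulation tests. LFTs up to 2X". Only the list for the type 2 diabetic population prints the word normal before electrolytes. No list names phosphorus or phosphate.

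In Section 6.a, Visit 1 has "screening tests (CBC, chemistry, lipid profile, HbA1c, PT, PTT, UA, pregnancy test if applicable", with the chemistry panel not itemised. Visit 3 has phosphate among its laboratory tests and a further sentence: "Serum phosphorus also will be measured". For Visit 4 the text says: "Labs for analyses as in Visit 3 are repeated". Randomisation follows completion of Visit 4. The Analyses paragraph schedules phosphate at Visits 3, 4, 5 and 6.

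**The concern.** An eligibility condition normally belongs in the eligibility list, because that is what staff work from when they clear a subject. Here the condition appears only in a risk table. The contrast within that table makes this look like an oversight. The gastrointestinal precaution from the same cell was carried into all three exclusion lists ("gastrointestinal surgery or gastrointestinal obstruction within two years" for the lean and obese nondiabetic populations, "surgery or gastrointestinal obstruction within two years" for the diabetic population), and so was allergy to sevelamer. Phosphorus was not.

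The visit flow adds to the doubt. Subjects are called eligible at Visit 2, before phosphorus is first named as a measurement at Visit 3, and no limit is attached to the result. If staff worked from Section 4.c alone, a subject with abnormal phosphorus could be randomised, possibly to sevelamer. At stake is consistency between a safety commitment and the working criteria.

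**Working it through.** There is no figure to reproduce: the point depends on no alpha, power, effect size, variance or dropout rate. The check is a reading of every place where the condition could appear.

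**Where phosphorus or phosphate is named**

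| Place | Count |
|---|---|
| Inclusion lists, Section 4.c | 0 of 3 |
| Exclusion lists, Section 4.c | 0 of 3 |
| Screening-test lists (Visit 1 in Section 6.a; eligibility rows of table 6.d) | 0 of 2 |
| Randomisation statements (Section 3, Section 6.a, Abstract) | 0 of 3 |
| Enrolment condition in Section 6.c | stated |
| Scheduled measurements (Visits 3, 4, 5, 6) | 4: two before randomisation, two on treatment |

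**Step 1: is there a conflict of rules?** Section 6.c limits enrolment to subjects with normal phosphorus. Section 4.c is silent. No list admits a subject whom Section 6.c would turn away on the ground of phosphorus. Both sections belong to one protocol, so a subject must satisfy both.

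**Step 2: is the item certainly absent from the lists?** The word is absent, but that does not settle whether the requirement is. All three inclusion lists have an electrolytes item, and the screening panel has an un-itemised chemistry test. Either could include phosphate, and the documents do not say which is meant. The missing word normal for the first two populations looks clerical, since a bare list of tests sets no criterion.

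**Step 3: can the condition be applied in time?** Visit 4 falls 7 to 21 days after Visit 3, and randomisation comes after Visit 4. The Visit 3 phosphorus result is therefore drawn at least 7 days before randomisation. The use of the word eligible at Visit 2 does not close screening: the oral glucose tolerance test performed at that visit is itself needed for the glucose-tolerance criteria, so eligibility is still provisional then.

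**Step 4: what does the silence at randomisation show?** The randomisation statements in Sections 3 and 6.a ask only that the Visit 4 studies be complete, and the Abstract attaches no condition. None mentions the glucose tolerance result, or the pregnancy test repeated at Visit 4, although both are listed criteria. Having 0 of 2 pre-randomisation phosphate measurements tied to randomisation therefore reflects how the passage is written. It does not show that this precaution was dropped.

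**Step 5: what would change?** Phosphorus enters no hypothesis test, power calculation or group-size statement in Section 6.a. The documents give no rate of abnormal phosphorus, so the number of subjects affected cannot be estimated from them.

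**The case for a change.** The strongest reply is that a condition outside the criteria list is easily missed. The protocol's own habit is to put sevelamer-specific conditions in Section 4.c: the gastrointestinal item and the allergy item are each in 3 of 3 lists. Phosphorus is the exception, no limit is given, and phosphate is scheduled under Analyses next to research markers, so a monitor has no single line against which to confirm that the condition was met. Repeating it would cost a line or two and no extra sample.

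The facts in this stand. The lists do not name phosphorus, and the documents do not say that electrolytes or chemistry covers it. What does not follow is that the plan lacks the rule. A breach would require staff to disregard an explicit sentence in their own protocol, and the result needed to honour that sentence is already collected in time. The documents also describe the check as additional to other protection: creatinine is capped in all three populations, and phosphate is followed on treatment at Visits 5 and 6. Writing the rule a second time would be tidier drafting, but it would not alter who should be enrolled.

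**Conclusion.** The observation is accurate, but it is a gap in cross-referencing that a team following the whole protocol would fill sensibly. The condition is stated once, contradicted nowhere, and can be checked from a sample taken at least 7 days before randomisation. The effect on endpoints, sample size, power and conclusions is nil.

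This rests on two readings. The first is that Section 6.c binds as part of the protocol. The second is that enrolment in that sentence includes the step of randomisation, so that the Visit 3 result can serve. If enrolment meant an earlier point, the condition would rest on the Visit 1 chemistry panel, whose contents the documents do not list. The limit for a normal value and any action on an abnormal one are clinical matters on which this review takes no position. No change to the plan is called for.
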